7.0 Study Endpoints:**Primary Endpoints**

Phase I: Mean difference in inter-beacon distance (in millimeters) (at time of 4DCT simulation compared to fractions 1,2, and 3 of SABR)

Phase 2: Mean within patient difference in PTV volumes of standard ITV-based SABR compared to gated SABR utilizing Calypso based PTV margins (expressed as a percentage difference).

Secondary Endpoints:

- 1) Patient self-reported quality of life (EORTC QLQ - LC13 questionnaire)
- 2) Acute and late toxicity - Common Terminology for Criteria for Adverse Events (CTCAE version 4.0)
- 3) Median within patient difference in radiotherapy doses to thoracic Organs at risk
- 4) Median change in FEV1, DLCO, and 6 minute walking distance on room air at baseline compared to follow-up time points.
- 5) Local tumor control (using the RECIST version 1.1 Criteria²⁶)
- 6) Progression Free Survival
- 7) Cancer Specific Survival
- 8) Overall Survival

8.0 Pre-treatment Investigations:

All staging investigations shall be completed within 12 weeks prior to study enrollment.

- 1) History and Physical Exam
- 2) CT scan or MRI of brain
- 3) PET scan
- 4) CT chest and abdomen
- 5) Pulmonary function testing (including spirometry, diffusion capacity, and 6 minute walk test)
- 6) CBC, electrolytes, BUN, Creatinine
- 7) Quantitative beta-HCG (Only if the participant is a premenopausal female).

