APPENDIX I – EORTC QLQ - LC13 Quality of Life Questionnaire (Lung Cancer)

APPENDIX II – Common Terminology Criteria for Adverse Events (CTCAE) version 4.0

1.0 Study Schema

This trial is a seamless phase I/II prospective, single arm, cohort study.

Phase I of the trial will consist of two patients and will serve to conduct quality assurance assessments and to familiarize thoracic surgeons, radiation oncologists, and medical physicists at CancerCare Manitoba and Health Sciences Center in the use and work flow of the Health Canada approved endobronchial implanted real-time tumor tracking transponder beacons (The Calypso™ beacon). Patients in phase I will undergo standard stereotactic ablative radiotherapy (SABR) of a lung tumor with prior endobronchial transponder beacon placement. For phase I, the transponder beacons will be used for comparative localization analyses and SABR treatment setup procedures will be carried out independent of transponder beacon data, however, transponder data will be collected in order to conduct, post-treatment, *in vivo* quality assurance assessments of beacon performance characteristics. Otherwise, the SABR treatment for phase I will consist of the currently accepted standard internal target volume based and standard image guided SABR.

Phase II of this trial will consist of 26 patients who will undergo a specialized form of SABR radiotherapy specifically designed to take full advantage of the real-time tumor tracking ability of the Calypso™ transponder beacons. Specifically, SABR in phase II will consist of smaller radiotherapy treatment volumes employing respiratory gating and smaller planning target volume expansion margins given the superior tumor location telemetry afforded by the Calypso™ beacons. Comparative dosimetric analyses contrasting the traditional ITV/PTV style treatments to those with reduced ITV/PTV margins achieved via Calypso guided SABR will be performed. Patient self-reported quality of life and toxicity assessments will be collected with the goal of facilitating power and sample size calculations for the design of a larger phase III randomized controlled trial of Calypso guided SABR treatment in the future.

Phase I (n=2)

Adults ≥ 18 years of age
T1N0M0 or T2N0M0 (<4cm) NSCLC; or
A single Metastatic Lung Tumor < 4cm
ECOG performance status 0 to 2
Surgically inoperable
Non-Oxygen dependent at baseline

“Standard” Stereotactic Ablative Radiotherapy:

- 1) Endobronchial Calypso Beacon Placement

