The anchored Calypso™ lung tracking beacon is a grain-of-rice sized transponder beacon (Figure 4) which is placed immediately adjacent to a lung tumor using a flexible bronchoscope. Typically three beacons are placed in the small airways of the lung (2 to 2.5 mm diameter airways) adjacent to the target tumor (within 3 cm of the tumor)²⁴. The Calypso beacon can be used as either a traditional radiopaque fiducial marker (which can be identified using standard kilovoltage x-rays, fluoroscopy, or CT scans) or as a passive electromagnetic beacon transponder. Each beacon measures 2 mm in diameter and 8 mm in length (14mm including the anchoring legs) and consists of a miniature electrical circuit that is encapsulated in a sealed biocompatible glass capsule. In order to prevent the beacon from migrating within the airways, the beacon has an affixed five-legged anchoring system which expands to 5mm in diameter once deployed from the Calypso lung catheter. The Calypso transponder beacon is placed endobronchially using the working channel of a bronchoscope and the Calypso lung catheter (Figure 5). Navigational bronchoscopy can be used to pre-plan the optimal location for each beacon to be placed within the airways by using a pre-bronchoscopy CT scan.

FIGURE 4: The Calypso™ Anchored Transponder Beacon with legs completely constrained (left), and deployed (right).

[figure not shown]
[figure not shown]
[figure not shown]

Figure 5: The single use Calypso Lung Catheter (for use in the working channel of a bronchoscope)

The transponder's electrical circuit is passive and the beacon does not contain an internal energy source. The transponder only emits a radiofrequency (RF) signal when it is excited by a harmless, non-ionizing RF field generated by the Calypso array (Figure 6). After RF excitation, each transponder briefly emits a response signal at a unique frequency that is specific to each beacon. This signal is detected by the sensor array with a refresh rate of 25 times per second (25 Hz). The Calypso system uses this information from all of the beacons to continuously determine the three dimensional location of the tumor isocenter relative to the linear accelerator's isocenter. This allows for real time monitoring of a lung tumor's motion during radiation treatment delivery.

Figure 6: Calypso system components

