- 4) ECOG performance status of 0 to 2.
- 5) Minimum life expectancy of 6 months.
- 6) Deemed fit to undergo bronchoscopy by their participating thoracic surgeon
- 7) Deemed fit to undergo SABR by their participating Radiation Oncologist.
- 8) Respiratory function (a patient must satisfy both “a” and “b” below):
 - a. Minimum FEV1 of 0.8 liters
 - b. Minimum DLCO of 35% predicted.
- 9) Able to provide written informed consent and understand verbal instructions necessary for radiotherapy treatments.

Exclusion Criteria:

- 1) Tumors located < 1 cm from the chest wall based on CT imaging.
- 2) Tumors located ≤ 2 cm from the proximal bronchial tree (see figure 7)
- 3) Patients who require supplemental oxygen at rest.
- 4) Patients who are unable to lie flat or still for a minimum of 30 minutes.
- 5) ECOG performance status 3 or 4.
- 6) Evidence of uncontrolled extra-thoracic metastatic disease (based on imaging or clinical findings).
- 7) Proven or suspected intrathoracic lymph node involvement.
- 8) Prior SABR to the target tumor.
- 9) Prior history of idiopathic pulmonary fibrosis, interstitial lung disease, or active collagen vascular disease (systemic lupus erythematosus, Rheumatoid arthritis, or Scleroderma)
- 10) Pregnancy.
- 11) Active pulmonary infection
- 12) Known hypersensitivity to nickel titanium (Nitinol)
- 13) Known Bronchiectasis of the small airways nearest to the tumor

Figure 7: The proximal bronchial tree (tumours within this region are ineligible for trial participation).**6.0 Study Objectives:****Phase I:**

- 1) To allow for members of the interdisciplinary care team (Thoracic surgeons, Radiation Oncology, Radiation Therapists, and Medical Physicists) to familiarize themselves with the clinical use of implanted endobronchial tumor tracking beacons and carry out quality assurance assessments in preparation for the subsequent phase II component of the study.
- 2) To quantify the presence (if any) of beacon migration (inter-beacon distance) at different time points in a patient's care path (time of implantation, CT simulation scan, and days of SABR treatment).
- 3) To assess the quality of life of patients having Calypso placement (EORTC QLQ - LC13 questionnaire)
- 4) To assess acute toxicity of beacon implantation using the Common Terminology for Criteria for Adverse Events (CTCAE version 4.0)

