- 5) To quantify the potential benefit of continuous monitoring of tumor location using Calypso by comparing it to traditional imaging-based setup.

Phase II:

- 1) To quantitatively assess the differences in irradiated treatment volumes and radiotherapy dose volume metrics for the PTV and healthy thoracic organs at risk between Calypso™ guided respiratory gated SABR and the traditional ITV based radiotherapy.
- 2) To serially quantify the acute and late toxicity of patients undergoing Calypso™ guided SABR using the Common Terminology Criteria for Adverse Events (CTCAE) Version 4.0
- 3) To serially quantify the self-reported quality of life of patients undergoing Calypso Guided SABR using the EORTC QLQ - LC13 questionnaire
- 4) To serially biobank blood and urine samples for patients undergoing radical SABR of lung tumors to allow for the future development of novel prognostic and predictive biomarkers for patients undergoing SABR.
- 5) To serially quantify changes to pulmonary function following SABR treatment

- 6) To demonstrate the benefit of Calypso treatments in reducing patient-specific component of PTV margins

Study Hypotheses:

Phase I: Calypso beacon placement will be safe and well tolerated and will function within their specified tolerances with minimal (sub-millimeter) inter-beacon migration.

Phase II: The Median Planning Target Volume (PTV) of Calypso guided respiratory gated SABR will be 40% smaller than the median PTV volume of standard ITV based SABR treatment with standard PTV margins. Furthermore, thoracic organs at risk will receive significantly less radiotherapy dose when compared to the standard SABR treatment.

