10.0 Treatment

Calypso Beacon Placement:

Calypso beacon placement will be performed using flexible bronchoscopy under general anesthesia or conscious sedation. The site of implantation will be localized using a combination of direct visualization, fluoroscopy, ultrasound and electromagnetic navigation bronchoscopy. Drs. [name] and [name] have received formal course training on the use of SuperDimension Navigational Bronchoscopy System for localization of lung nodules and directed bronchoscopic placement of implant devices. This will greatly facilitate accurate beacon placement. The bronchoscope will be advanced under direct vision into the targeted implantation site. Using navigational bronchoscopy and fluoroscopy the target implant sites will be identified and guide sheath placed through the bronchoscopy working channel. Through the guide sheath, the catheter with anchored beacon transponder will be directed to the implantation sites under bronchoscopic and fluoroscopic direction. The beacon transponders will be deployed until properly anchored in the appropriate peri-tumoral implantation sites. Satisfactory beacon placement will be verified using fluoroscopy. The anchored transponders are implanted in a triangle around the tumor target and are at least 1 cm but no more than 7.5 cm from each other. Although navigational bronchoscopy is recommended for beacon placement, conventional bronchoscopy with fluoroscopic guidance is also acceptable for beacon placement at the discretion of the attending thoracic surgeon in the event that navigational bronchoscopy is unavailable on the day of the beacon placement procedure.

Radiotherapy:

4-Dimensional CT simulation Scan: Patients will be simulated in the supine position and immobilized using a Vac-lok bag with arms raised above their heads and with legs on a knee rest for comfort. Patients will be free breathing with a relaxed tidal breathing pattern. The CT simulation scan will be performed using the Varian RPM system in order to produce 10-respiratory phase correlated CT data sets (4-DCT scan). Intravenous contrast is not required.

Co-registration of PET scan: For purposes of contouring the primary tumor, PET scan fusion is recommended but not mandatory.

Organ at Risk Delineation: The following organs at risk will be contoured on the CT_{average} dataset:

- 1) Normal Lung;
- 2) Esophagus;
- 3) Chest wall (within 5 cm of the PTV);

- 4) Ribs (within 5 cm of the PTV);
- 5) Heart;

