Radiotherapy treatment planning: SABR treatment plans will be calculated using the Varian Acuros dosimetric algorithm with inhomogeneity correction. Two co-planar, two-hundred and forty degree arcs of volumetric modulated arc therapy (VMAT) will be the default beam arrangement.

SABR Delivery: SABR will be delivered using the Varian Edge linear accelerator at the KIAM using 10MV flattening filter free photon beams using a dose rate of 2400 MU/min.

Gating Window: The end-exhalation phase (CT50) plus one phase directly preceding (CT40) and following (CT60) will be used as the gating window. CT30 and CT70 may also be included in the gating window.

Chemotherapy: Chemotherapy, immunotherapy, or mutation targeted therapies should be held at least 24 hours prior to the first fraction, and can be restarted 24 hours after the delivery of the last fraction.

Cone Beam CT-based (CBCT) Image Guidance: In phase I of the trial, cone beam CT scans will be performed daily in order to allow for initial image guidance of treatment setup using bony landmarks (vertebral bodies) and soft tissue (tumour). Calypso beacon data will be collected during phase I including inter-transponder geometry.

Calypso Guidance: In Phase II of the trial, calypso beacon data will be used to fine tune initial patient positioning and treatment delivery. The location data from the Calypso beacons will be captured by the Calypso array in order to assess inter-transponder beacon distance, as well as beacon geometric center location relative to the linear accelerator's isocenter. This position is used as the reference for Calypso to provide continuous monitoring. Calypso data will then be used for respiratory gating of the SABR treatment. CBCT imaging may also be performed to verify the soft tissue-beacon correspondence. CBCT images will be evaluated and may be used for patient repositioning if necessary.

Respiratory gating (phase I): For phase I of the trial, the respiratory gating signal will not be used to control the radiation beam delivery, however, Calypso transponder beacons will be used to provide location telemetry for quality assurance and data analysis purposes only.

Respiratory Gating (Phase II): The SABR radiation beam delivery will be gated using the Calypso transponder location data for phase II of the study.

OAR Tolerances (as derived from the RTOG 0618 protocol by Timmerman et. al.):

| Organ | Volume | Dose Constraint (Gy) |

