MRI compatibility: Anchored Calypso beacons can be safely scanned using MRI with either a 1.5 or 3.0 Tesla static magnetic field with or a magnetic field gradient of up to 9.3 Tesla/meter without inducing any clinically significant displacement force or torque. An MRI image artifact may extend up to 2 cm from the anchored transponder, which is of no clinical significance for patients on this trial since, outside of research studies, MRI is not used in the routine diagnosis of intrapulmonary lesions.

Retrieval of Calypso Beacons:

If an unanticipated adverse effect occurs with a Calypso beacon and removal of the beacon is required, then the anchored beacons can be retrieved using a flexible bronchoscope and forceps similar to other endobronchial foreign body retrievals.

12. 0 Evaluation During and After Protocol Treatment

| | Baseline | 4DCT Sim* | Each SABR Fraction[¶] | 2 mo[#] | 6 mo | 12 mo | 18 mo | 2 yr | 3 yr |
|------------------------------------|------------------------|-----------------------------|--|------------------------------------|------------------------|-------------------------|-------------------------|--------------------|--------------------|
| History & Physical Exam | x | | | x | x | x | x | x | x |
| CT or MRI Brain | x | | | | | | | | |
| CT Chest & Abdomen | x | | | | x | x | x | x | x |
| PET Scan | x | | | | | | | | |
| Chest X-ray | | | | x | | | | | |
| Pulmonary | x | | | | x | | x | | x |

| Function Testing | | | | | | | | | |
|--------------------------------|---|---|---|---|---|---|---|---|---|
| 6 min walking test | x | | | | x | | x | | x |
| Medication Profile | x | | | x | x | x | x | x | x |
| CBC, Lytes, Bun, Cr | x | | | | | | | | |
| EORTC QLQ - LC13 | x | x | x | x | x | x | x | x | x |
| Toxicity Profile (CTCAE V 4.0) | x | x | x | x | x | x | x | x | x |
| Inter-beacon distance | | x | x | | | | | | |

Notes:

* 4DCT is to be performed no later than 4 calendar weeks after the date of beacon implantation

φ The first fraction of SABR is to start no later than 14 calendar days after the 4DCT simulation scan

the timing of all follow up evaluations are relative to the date of the last fraction of SABR.

13.0 Statistical Considerations:Descriptive characteristics:

Baseline patient, tumor, and treatment characteristics will be summarized using standard descriptive statistics as summarized in the table below.

| Patient Factors | |

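### On its plain reading, the Phase I primary endpoint lets opposite changes in inter-beacon distance cancel, so it cannot properly test the sub-millimetre migration hypothesis

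*Combined protocol and SAP*

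**What the plan says.** The Phase I primary endpoint in Section 7.0 is "Phase I: Mean difference in inter-beacon distance (in millimeters) (at time of 4DCT simulation compared to fractions 1,2, and 3 of SABR"). The hypothesis it serves, under Study Hypotheses in Section 6.0, is that the beacons "will function within their specified tolerances with minimal (sub-millimeter) inter-beacon migration". The matching objective in the same section is "To quantify the presence (if any) of beacon migration (inter-beacon distance) at different time points". Section 1.0 states "Phase I of the trial will consist of two patients".

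The number of distances follows from the implant description. The Background says "Typically three beacons are placed in the small airways of the lung", which gives three pairwise distances per patient. Section 10.0 has the beacons in a triangle around the tumour and says they "are at least 1 cm but no more than 7.5 cm from each other". On data capture, the same section states "Calypso beacon data will be collected during phase I including inter-transponder geometry". The Section 12.0 schedule has a row "Inter-beacon distance", marked at 4DCT simulation and at each SABR fraction, with no restriction by phase.

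Section 13.0 has no entry for this endpoint. The change formulas it does give, for PTV, organ-at-risk metrics and lung function, are plain subtractions divided by the reference value, with no absolute value taken. Nothing in the document states which statistic is to be compared with 1 mm.

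**The concern.** Migration is a question of magnitude. A beacon that has moved matters whether a given pair distance has grown or shrunk. In a triangle, one beacon moving sideways lengthens one of its distances and shortens the other, while the third stays the same. Averaging those changes with their signs removes most of the signal. Averaging again over fractions and patients allows further cancellation.

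An endpoint computed this way could read as sub-millimetre, and so appear to support the hypothesis, when individual distances have changed by several millimetres. It would also leave a choice between signed and absolute summaries to be made after the data are seen, for a primary endpoint.

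**Working it through.** **Plan's own figure.** There is none to reproduce. The only power statement, in Section 13.0, concerns PTV volume.

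**Inputs from the protocol.** Three beacons, spacing 10 to 75 mm, two patients, and a threshold of 1 mm taken from the word sub-millimetre. **Assumptions.** An equilateral triangle, the sizes of the shifts, and the SDs below. The documents give none of these.

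**1. One beacon shifted sideways.** Let the side be L and let one beacon move m parallel to the opposite side. The two distances from that beacon become √(L² + Lm + m²) and √(L² − Lm + m²). The third is unchanged. For L = 30 and m = 5:

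- √1075 − 30 = +2.79 mm
- √775 − 30 = −2.16 mm
- third pair: 0
- signed mean = (2.79 − 2.16 + 0)/3 = 0.21 mm
- mean absolute change = (2.79 + 2.16 + 0)/3 = 1.65 mm

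Over the permitted spacing, with m = 5 mm:

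| Spacing (mm) | Pair changes (mm) | Signed mean | Mean absolute | Largest |
|---|---|---|---|---|
| 10 | +3.23, −1.34, 0 | 0.63 | 1.52 | 3.23 |
| 30 | +2.79, −2.16, 0 | 0.21 | 1.65 | 2.79 |
| 75 | +2.62, −2.37, 0 | 0.08 | 1.66 | 2.62 |

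At 30 mm spacing, shifts of 2 and 3 mm give signed means of 0.03 and 0.08 mm, mean absolute changes of 0.67 and 1.00 mm, and largest changes of 1.05 and 1.61 mm.

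**2. Six independent distances (three pairs, two patients), each change normal with mean 0 and SD s.** The signed mean has SD s/√6, so P(|signed mean| < 1 mm) = 2Φ(√6/s) − 1. For s = 2 this is 2Φ(1.225) − 1 = 0.78. The mean absolute column was simulated.

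| SD (mm) | Signed mean below 1 mm | Mean absolute below 1 mm |
|---|---|---|
| 1 | 99% | 80% |
| 1.5 | 90% | 32% |
| 2 | 78% | 11% |
| 3 | 59% | 2% |

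**3. Correlated distances.** The sides of one triangle share beacons, so independence is only approximate. A simulation on the triangle itself (30 mm, two patients, one beacon in each moved in a random direction, shift constant over fractions) gives the following for moves of 2, 3 and 5 mm:

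- signed mean below 1 mm: 98%, 83% and 56% of runs
- mean absolute change below 1 mm: 96%, 52% and 7% of runs

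**4. Noise in the maximum.** Assume no migration and a measurement SD of 0.2, 0.3, 0.4 or 0.5 mm per distance, with the 4DCT value shared by the three fractions. The largest of the nine absolute changes per patient reaches 1 mm in 0.4%, 14%, 46% or 73% of patients.

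**The case against.** The strongest reply is that the protocol never says signed. That is true. The objective of quantifying any migration fits an absolute reading, so a reader who infers that the protocol prescribes a signed mean goes further than the text. The signed reading rests on the ordinary meaning of a mean difference and on the form of the Section 13.0 formulas. If absolute values were intended, the same clarification is needed.

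Second, sign is only part of the difficulty. For a 2 mm shift of one beacon, averaging dilutes the signal almost as much as cancellation does (98% against 96% of runs below 1 mm). This stands. It is why the maximum should be shown as well. Sign matters clearly at 3 and 5 mm.

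Third, a maximum judged against 1 mm could mislead in the other direction, as step 4 shows. This also stands, and it argues against making the maximum the criterion.

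Fourth, Section 11.0 cites a migration rate of 1% for anchored beacons, so shifts in every beacon may be unlikely. The scenarios illustrate how the statistic behaves and do not predict how often migration will occur.

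Finally, a reader might infer that Phase II opens on the strength of this mean and would be falsely reassured. The documents do not support that. No rule ties Phase II to the result, and Phase I is a familiarisation and quality-assurance stage. Individual beacon geometry is recorded. In Phase II, Section 10.0 has inter-beacon distance assessed again and allows cone-beam CT checks. Nor is the measurement confined to two patients; only the primary-endpoint label is.

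**Conclusion.** The point holds as a defect in how the endpoint is defined. Sign, aggregation and the statistic held to 1 mm are all unstated. On the plain reading, the summary can meet the sub-millimetre hypothesis while a beacon has moved 5 mm. In the worked example it understates the mean absolute change by 0.9 to 1.6 mm (1.52 − 0.63 to 1.66 − 0.08). That size depends on the assumed triangle, direction and shift. The probabilities depend heavily on the assumed SD and should be read only as a range.

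The practical effect is limited, because the underlying distances are collected and absolute changes can be derived from them. Two further inferences should not be drawn:

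- Two patients are too few to characterise a migration rate, but the protocol does not set out to estimate one. The Phase I result should simply be presented as descriptive.
- Distances may vary with breathing, and the protocol does not name the 4DCT phase to be used as reference. The documents give no size for this effect, so it is a matter of specification and not a demonstrated bias.

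**What to change.** In Section 7.0, with a matching entry in Section 13.0:

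- Define the endpoint as the absolute change in each beacon-pair distance from 4DCT to each of fractions 1, 2 and 3, using the same stated respiratory phase where available.
- Report the mean absolute and the maximum absolute change per patient and per fraction.
- State that the 1 mm figure applies to the mean absolute change. Show the maximum descriptively beside the measurement error of a distance.
- Describe the two-patient Phase I result as descriptive only.
- Tabulate the same measure for all 28 patients.

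The cost is revised wording and one extra table, with no new data collection. There are two drawbacks. The maximum is sensitive to measurement noise. The mean absolute change still dilutes a small shift of a single beacon (0.67 mm for a 2 mm shift at 30 mm spacing). Each therefore needs the other beside it.

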3.0 Trial Design

This is a prospective, single arm, seamless phase I/II cohort study (investigator initiated trial) with a planned total accrual of 28 patients.

4.0 Study Population:

Potentially eligible patients are adults with surgically inoperable, biopsy proven or suspected single T1N0 or T2N0 Non-small cell lung cancer tumor or patients with a single pulmonary metastasis (<4 cm maximal tumor dimension) from a known primary malignancy of any histology (either metastatic failure to a single pulmonary site after primary radical treatment, or metastatic progression to a single lung metastasis following palliative chemotherapy with no other sites of uncontrolled disease). Tumors should be located either in the lower lobe, lingula, or right middle lobe of the lung however, patients with upper lobe tumors are eligible as long as the tumors have a respiratory amplitude of ≥ 1 cm. Tumors should be located at least 2 cm from the proximal bronchial tree (non-central tumors).

5.0 Eligibility Criteria:

- 1) Adult ≥ 18 years of age who is surgically inoperable, or refusing surgical management.
- 2) Tumor criteria (a patient must satisfy one of “a”, “b” below to be eligible):
 - a. AJCC 7th edition clinical T1aN0M0, T1bN0M0, or T2aN0M0 (<4cm) Non-small cell lung cancer (adenocarcinoma, squamous cell carcinoma, or NSCLC Not Otherwise Specified) of the middle or lower lobes of the lung*;
 - b. A single pulmonary metastasis (<4cm) of a known primary malignancy of any histology involving the middle or lower lobes of the lung* (either metastatic failure to a single pulmonary site after primary radical treatment, metastatic progression to a single lung

[figure not shown]
metastasis following palliative chemotherapy, or a single pulmonary metastatic lesion of newly diagnosed stage IV malignancy).

*upper lobe tumors are eligible for trial participation if the tumor has a demonstrated tumor motion of ≥ 1 cm in any axis (as assessed by fluoroscopy at the time of bronchoscopy).

- 3) Confirmation of malignancy (a patient must satisfy one of “a”, “b” below to be eligible):
 - a. Tumors accessible by bronchoscopy, image-guided percutaneous biopsy, or other invasive staging methods require biopsy confirmation of malignancy.
 - b. If a tumor is not amenable to a diagnostic biopsy, evidence of growth of the target tumor on serial imaging scans is necessary prior to enrollment. An increase in SUV of the target tumor on serial PET scans is also acceptable.

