9.0 Study Enrollment Procedures

Participating investigators are responsible for confirming the eligibility/ineligibility status of a potential study participant prior to enrollment. Since this trial requires the active participation of both thoracic

surgeons and radiation oncologists, a patient should be assessed by both specialists prior to being offered participation in the trial.

Potentially eligible patients will be offered voluntary participation in this trial by their participating physician. Patients will be given an informed consent form to review and will be contacted at a later date by trial personnel to answer any questions which may arise and to obtain written informed consent.

Patients who have consented to trial participation will then undergo all required pre-treatment investigations (if not already done) in a timely manner.

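### The only pregnancy test is not timed to any irradiation: even one taken on the day of beacon implantation can be 42 days old at the first SABR fraction

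*Combined protocol and SAP*

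**What the plan says.** Pregnancy is exclusion 10 in section 5. The supporting test is the last of seven items in section 8: "Quantitative beta-HCG (Only if the participant is a premenopausal female". The only numeric timing rule in that section is "All staging investigations shall be completed within 12 weeks prior to study enrollment".

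Section 9 adds two rules. Eligibility is settled before entry: "Participating investigators are responsible for confirming the eligibility/ineligibility status of a potential study participant prior to enrollment". Outstanding tests follow consent, and existing results are accepted: "Patients who have consented to trial participation will then undergo all required pre-treatment investigations (if not already done) in a timely manner". No section limits the time from enrolment to beacon implantation.

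Section 10 uses fluoroscopy to guide and verify beacon placement, then a 4DCT simulation, then 54 Gy in 3 fractions. The notes to section 12 set the remaining intervals: "4DCT is to be performed no later than 4 calendar weeks after the date of beacon implantation" and "The first fraction of SABR is to start no later than 14 calendar days after the 4DCT simulation scan".

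The other six items in section 8 each have a row in the section 12 table. The only laboratory row is "CBC, Lytes, Bun, Cr", at baseline. Beta-HCG has none.

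**The concern.** An exclusion for pregnancy in a radiotherapy trial is meant to hold when the patient is irradiated, not only when she enrols. This protocol anchors its one test to enrolment at best, while the exposures come later and over a span of weeks. A premenopausal woman who meets every stated timing rule could have fluoroscopy, 4DCT and SABR on a negative result too old to show that she is still not pregnant. Nothing in the schedule prompts staff to test again, and pregnancy is not among the listed reasons in section 16 for stopping protocol treatment.

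Such women can enter. The minimum age is 18, and section 5 admits "A single pulmonary metastasis (<4cm) of a known primary malignancy of any histology", so the population is not confined to older patients with primary lung cancer.

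**Working it through.** The protocol states no figure for the age of the test, so there is none to reproduce. The check adds the intervals that the protocol permits.

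Inputs:
- Test to enrolment, if the section 8 window applies: at most 12 weeks = 84 days.
- Enrolment to implantation: no limit stated; call it g.
- Implantation to 4DCT: at most 4 weeks = 28 days (section 12 notes).
- 4DCT to fraction 1: at most 14 days (section 12 notes).

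**Step 1: the figure that does not depend on how section 8 is read.** Suppose the test is taken on the day of implantation. Its age can be 28 days at 4DCT and 28 + 14 = 42 days at fraction 1. A test taken on the enrolment day with g = 0 gives the same result.

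**Step 2: the 12-week window covers beta-HCG.**
- Age at implantation = 84 + g
- Age at 4DCT = 84 + g + 28
- Age at fraction 1 = 84 + g + 28 + 14 = 126 + g

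| g (assumed) | At implantation | At 4DCT | At fraction 1 |
|---|---|---|---|
| 0 | 84 days (12 weeks) | 112 days (16 weeks) | 126 days (18 weeks) |
| 2 weeks | 98 days (14 weeks) | 126 days (18 weeks) | 140 days (20 weeks) |
| 4 weeks | 112 days (16 weeks) | 140 days (20 weeks) | 154 days (22 weeks) |
| 8 weeks | 140 days (20 weeks) | 168 days (24 weeks) | 182 days (26 weeks) |

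The row g = 0 assumes no delay after enrolment. It is not a ceiling, because g is unbounded. The other values of g are illustrations; the documents give no typical delay.

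**Step 3: the 12-week window does not cover beta-HCG.** No numeric window is then left. Section 9 asks only for promptness, and only for tests not already done.

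**Step 4: which exposures need their own test.** If tests were required only within 7 days before implantation and within 7 days before fraction 1, a result could still be 7 + 28 = 35 days old at 4DCT. The 4DCT therefore needs its own requirement.

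The figures stop at fraction 1. Section 10 requires at least 40 hours between fractions, so fraction 3 comes at least 80 hours later; this is not added above.

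**The case against.** The strongest reply is that the protocol already has the essentials. Pregnancy is an unconditional exclusion, a quantitative test is required, and the radiation oncologist must judge the patient fit for SABR. The trial has 28 patients who are inoperable or decline surgery, so few will be premenopausal. The missing row is partly layout: section 8 already requires the test, and a baseline row alone would change nothing. All of this stands and keeps the point minor. It does not close the gap, because none of these safeguards dates the test relative to an exposure. A department may test before radiotherapy as routine, but the documents do not say so.

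Some stronger readings are tempting and are not supported:
- A reader might infer that the protocol plainly permits an 18-week-old test. That needs the section 8 window to cover beta-HCG, but the sentence speaks of staging investigations and a pregnancy test is not one. The 84- and 126-day figures are conditional on that reading.
- A reader might take 126 days as the maximum. It is the value for zero delay after enrolment, and that interval is not capped.
- A reader might infer a quantified risk to a fetus. The documents give no pregnancy rate and no fetal dose from thoracic fluoroscopy, 4DCT or lung SABR.
- A reader might conclude that pregnancy and contraception are addressed nowhere else. The consent pages were removed before review and cannot be assessed.
- A reader might extend the point to the lung-function baseline. The documents give no rate of decline, so an old baseline shows only that some elapsed time precedes SABR, not a bias of any size.

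**Conclusion.** The point holds as a minor safety improvement. The firm finding is that beta-HCG has no window tied to irradiation and no repeat, so a test taken as late as implantation day can be 42 days old at fraction 1. This rests only on the two interval limits in section 12. The larger figures, 84 days at implantation and 126 days at fraction 1, apply if the 12-week window covers the test and implantation falls on the day of enrolment; any delay adds to both.

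All of these are cases the stated timing rules allow, not expected cases. The number of women affected is likely to be small, no event count can be given, and the PTV comparison that forms the primary endpoint is unaffected. The change is still worth making: the test is already required, and timing it properly is cheap.

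**What to change.** Add a beta-HCG row to section 12, for premenopausal women only. Require a negative result within a short fixed window before each of three events: beacon implantation, 4DCT and fraction 1. Seven days is a reasonable example; the sponsor should set the length. One test may serve two events if it falls within both windows.

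With a 7-day window, no result would be more than 7 days old at any of the three events, against the 42 days or more now possible at fraction 1.

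The cost is one table row and up to three inexpensive pregnancy tests in each of the few women concerned. No other assessment needs to change.
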